9.2.1 Duration of the study

Patients will be encouraged to participate in the registry and followed up to ten years after entry of the first patient or until definitive pump explanation whichever comes first.

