9.3.1.2 Pump pocket infection

Surgical interventions for pump implantation or catheter replacement as well as repeated transcutaneous punctures of the pump-pocket for insulin refills and investigation procedures on the implanted system can lead to an infection at the implantation site. This may be treated with antibiotics alone or include pump explantation. When hospitalization is required for pump explantation as part of the treatment, SAE must be reported.

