9.3.1.4 Skin Erosion

In extreme cases, an implanted device may erode through the skin, resulting in infection of the implant site and pump explanation. When hospitalization is required for pump explanation as part of the treatment, SAE must be reported.

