In addition, at three and six months after study entry, then every six months corresponding approximately to the period for four refill visits, all the following variables and relevant information will be collected since the last visit in the e-CRF:

- Reason for visits (planned and if not planned; metabolic or device problem since the last data collection),
- Concomitant medications, related to comorbidities, complications and diabetes treatment,
- Most recent urine microalbumin/creatinine ratio available every six months,
- Most recent HbA1c available every six months,
- Review of proper collection of adverse events over the last six months period as described above,
- Date of last rinsing procedure,
- Corrective actions (including subcutaneous insulin injection) in case of pump jamming, pump dysfunction and/or catheter occlusion occurs.

In case of study discontinuation, the following data will be collected:

- Date of discontinuation
- Reason for Study discontinuation (e.g., voluntary withdrawal, definitive pump explantation, death, lost to follow-up)

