9.6.3 Procedure for withdrawal of patients from study follow-up schedule

Participants may withdraw consent and discontinue participation in the study at any time, with no effect on their medical care or access to treatment. If a subject discontinues prior to completing the study follow-up period, any known reason for the discontinuation should be documented in the e-CRF. The participating investigators will make documented efforts (repeated phone calls, emails, contact to relatives, etc) to keep track of the patient, obtain information about the patient's health status and a reason for study withdrawal. Patients who continue on CIPII cannot be lost to follow up and must be followed at a certified center.

Pre-identified potential reasons for patient's withdrawal are: patient's withdrawal of consent, patient's or investigator's decision to stop CIPII and switch to another form of treatment, and death. If the patient is withdrawal from the study, following pump explanation in the context of the pump phase-out process, it will be clearly mentioned in the eCRF.

For patients who choose to stop CIPII, they are followed until any AE or SAE are recovered or stabilized. Once the pump has been discontinued and all AEs recovered or stabilized, no further information needs to be collected and the patient withdraws from the study.

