9.7.1 Primary analysis

Since the primary objective is to monitor the important identified risks (see Section 9.3.1 for primary endpoints definitions, the analysis will be descriptive and the multiplicity control will not be considered.

- For the important identified risks including severe hypoglycaemia, hyperglycaemia due to underdelivery of insulin, pump pocket infections, skin erosion, and abnormal wound healing, the time to first event will be depicted by the Kaplan-Meier methodology. Globally, the total number assessed will be given and the number and percentage of events/censored will be calculated. For each time point (six-month and each year time-points), the number of patients at risk, the number of events and the probability (Kaplan Meier estimates) of an event and its 95% confidence interval (CI) will be given.
- Graphically, the cumulative risk over the entire study using life table approach, as well as the instantaneous risk expressed as the hazard function over time, will be presented according to the time expressed in years and using a kernel smoothing method.

Moreover, a horizontal line will represent the incidence rate calculated, as number of patients with one or more events divided by the number of patients treated.

- For rare events, the incidence rate using time to event approach will be considered: number of patients with the event, total patients years for the event, and incidence rate per 100 patient-years with its 95% CI will be calculated.

For the analyses purposes, all AEs will be recorded in the study safety database and classified according to Medical Dictionary for Regulatory Activities (MedDRA® version 16.1 or later) by system organ class and preferred terms (PTs).

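### Kaplan-Meier and life-table estimates overstate the cumulative risk of the pump-dependent events, because death and definitive explantation without the event can only be handled as censoring

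*Protocol*

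**What the plan says.** Protocol Section 9.7.1 sets the primary analysis of the five important identified risks. At six months and at each year, "the probability (Kaplan Meier estimates) of an event and its 95% confidence interval (CI) will be given". Overall, "the number and percentage of events/censored will be calculated", so there are two outcome states and no third. The graphical summary shows "the cumulative risk over the entire study using life table approach", next to a smoothed hazard curve and a horizontal line at the crude proportion of treated patients with an event.

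Section 9.2.1 ends individual follow-up at ten years from the first patient's entry or "until definitive pump explanation whichever comes first" (the last noun is plainly meant as explantation). Section 9.6.2.3 records the "Reason for Study discontinuation (e.g., voluntary withdrawal, definitive pump explantation, death, lost to follow-up", and Section 9.6.3 foresees withdrawal for the "patient's or investigator's decision to stop CIPII and switch to another form of treatment, and death". Section 9.6.3 also has phase-out explantation marked in the eCRF.

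Three of the five risks are tied to explantation in their own definitions. On pump pocket infection: "This may be treated with antibiotics alone or include pump explantation" (Section 9.3.1.2). On skin erosion: "resulting in infection of the implant site and pump explanation" (Section 9.3.1.4). Section 9.3.1.3 mentions explantation as part of the treatment of abnormal healing. Neither Section 9.7 nor the limitations in Section 9.9 mentions competing events.

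**The concern.** After definitive explantation a patient cannot have a pocket infection, a skin erosion or hyperglycaemia from pump under-delivery. After death no event can occur. Kaplan-Meier and the life table nevertheless give these patients the future risk of those still on the pump. The result describes a population in which nobody dies or is explanted, while the label cumulative risk invites the reader to take it as the share of treated patients who have the event. The gap widens with time, so it is largest at the late yearly time points, and long-term safety is a stated reason for the study (Section 7.2).

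A second issue is dependence between endpoints. If explantation follows one complication, it removes the patient from the curves of the others. Patients prone to one complication may be prone to another, and the censoring is then informative.

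**Working it through.** The protocol states no event, death or explantation rate, so there is no figure to reproduce. All hazards below are assumptions.

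**Inputs from the protocol.** Pump life of seven years (Section 5, amendment 2); study duration of ten years (Section 9.1); about 260 patients (Section 9.5.1).

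**Step 1: which exits are censored.** The estimator recognises event and censored only. A patient who dies or is definitively explanted before the event is not an event, and so is censored.

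**Step 2: size under constant, independent hazards.** Let λ be the event hazard, c the hazard of death plus non-phase-out explantation, and T the time in years.

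- Limit of one minus Kaplan-Meier: 1 − exp(−λT)
- Actual cumulative incidence: λ/(λ+c) × [1 − exp(−(λ+c)T)]

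With λ = 0.03 and T = 7, the first is 1 − exp(−0.21) = 18.9%. With c = 0.02, the second is 0.6 × [1 − exp(−0.35)] = 0.6 × 0.2953 = 17.7%. Ratios below come from unrounded values.

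| c per year | 1 − KM, 7 y | Cumulative incidence, 7 y | Ratio | 1 − KM, 10 y | Cumulative incidence, 10 y | Ratio |
|---|---|---|---|---|---|---|
| 1% | 18.9% | 18.3% | 1.03 | 25.9% | 24.7% | 1.05 |
| 2% | 18.9% | 17.7% | 1.07 | 25.9% | 23.6% | 1.10 |
| 5% | 18.9% | 16.1% | 1.18 | 25.9% | 20.7% | 1.26 |

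At 7 years the ratios are nearly the same for λ = 0.01 (1.03, 1.07, 1.18) and λ = 0.05 (1.03, 1.07, 1.17).

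**Step 3: simulation.** With 260 patients, 1000 runs, λ = 0.03, c = 0.05 and 10 years, Kaplan-Meier averaged 26.0% and Aalen-Johansen 20.7% on the same data. The sampling SD of Kaplan-Meier was 3.0 points.

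**Step 4: dependent exits.** The event and the exit share a gamma frailty of variance 1, with mean λ = 0.05 and 10 years. The risk without any exits is 33.4%.

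| Mean c per year | Kaplan-Meier | Actual cumulative incidence |
|---|---|---|
| 2% | 31.6% | 29.4% |
| 5% | 29.3% | 25.1% |

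With dependence, Kaplan-Meier estimates neither the actual share with the event nor the risk without exits.

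**The case against.** The protocol writes no censoring rule for death or explantation, and Section 9.7 leaves the complete overview of analyses to the amended SAP, which is not at hand and could add a cumulative incidence analysis. That is true, but the protocol itself names the estimator and its two states. This is a stated choice, not a detail left open.

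Risk while on the pump is a legitimate target for a drug-device product. This also stands, but Section 9.7.1 does not define cumulative risk that way. Hazard curves and rates per 100 patient-years are not invalidated by competing events, and nothing here is held against them.

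The size is assumed, and the gap may be small against sampling error. At c = 2% the 7-year difference is 18.9 − 17.7 = 1.2 points, while a simple binomial 95% half-width at 19% with 260 patients is 1.96 × √(0.19 × 0.81/260) = 4.8 points. That limits the urgency, though a systematic error in one direction does not show in the interval.

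Three stronger readings are tempting and are not supported:

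- A reader might infer that explantation biases the curve of the event that caused it. It follows that event, so the first-event curve is unaffected; any dependence acts across endpoints.
- A reader might infer that explantation ends all five risks. Severe hypoglycaemia is defined in Section 9.3.1.1 without reference to the pump, and a patient who moves to another treatment can still have it. Abnormal healing arises from the implantation procedure, so late exits should matter little to it.
- A reader might infer a large bias. At c = 10% the same formula gives 13.8% against 18.9%, an excess of 37%, but nothing in the protocol supports such a rate.

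**Conclusion.** The point holds for the four pump-dependent risks: under-delivery hyperglycaemia, pump pocket infection, skin erosion and, less so, abnormal healing. For these, the estimator fixed in Section 9.7.1 gives more than the share of patients who have the event.

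The size depends on how often patients die or are explanted for reasons other than the phase-out, which the documents do not say. Up to about 1 per 100 patient-years the overstatement is about 5% relative or less, even at ten years. From about 2 per 100 patient-years it becomes material (7% at seven years, about 10% at ten). These figures assume constant, independent hazards. Informative censoring across endpoints is plausible from the definitions in Section 9.3.1, but its extent is unknown.

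Phase-out explantation is driven by supply and is close to administrative censoring, so it is not part of the problem. The change is worth making because these risks are the primary objective and the repair is cheap.

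**What to change.** - **Pump-dependent risks.** Report the Aalen-Johansen cumulative incidence with 95% CI at six months and each year. Competing events: death and definitive explantation for any non-phase-out reason. Censoring: phase-out explantation, withdrawal, loss to follow-up and end of study.
- **Failed pumps after supply ends.** Section 5 puts the end of supply at June 2019. A pump that then fails and cannot be replaced fits both device failure and phase-out. State its classification in advance, and show a sensitivity analysis with it classified the other way.
- **Severe hypoglycaemia.** Treat only death as competing, or define the target explicitly as first event while on the pump.
- **Retained displays.** Keep the cause-specific hazard plots and the rates per 100 patient-years. If Kaplan-Meier stays, label it as risk in the hypothetical absence of death and explantation.

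The cost is analysis wording, a second estimator to explain to readers, and one coded split of the explantation reason. Dates and reasons of discontinuation are already collected and phase-out exits already flagged, so no new visit or assessment is needed.

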All AEs will be followed until resolution or until the end of the follow-up period, whichever comes first.

Data Sources

Investigators at each site will collect and provide pre-specified data on study participants at baseline and during follow-up visits. Data elements provided by investigators and staff will be collected from information routinely recorded in the medical record, or will be prospectively recorded for the purposes of the study. No visits or examinations, laboratory tests or procedures are mandated as part of this study.

Information required to validate Serious Adverse Events (SAEs) will be requested from investigators and medical facilities as needed by the medical monitors, which may include confirmation of diagnoses or conditions and relatedness of AEs by the treating investigators, medical records including laboratory test results and imaging procedure results, and death certificates.

Study Size

This is a descriptive study that is not testing a hypothesis. As such, a formal sample size calculation is not performed. It is planned to recruit all patients who are willing to participate, from all trained investigators in certified centers in all participating European countries, and without a minimum designated for any country or region. The projected study size will be approximately 260 patients. No new patient or a very limited number of newly implanted patients is expected.

Data Analysis

Eligible patients will be those who have signed an informed consent form (ICF) and have received at least one dose of Insuman Implantable 400 IU/mL

• Primary analysis

Since the primary objective is to monitor the important identified risks, the analysis will be descriptive and the multiplicity control will not be considered.

For the important identified risks including severe hypoglycaemia, hyperglycaemia due to underdelivery of insulin, pump pocket infections, skin erosion, and abnormal healing, the time to first event will be depicted by the Kaplan-Meier plot. The cumulative event rate and its 95% confidence interval (CI) will be presented yearly.

The cumulative risk over the entire study and the instantaneous risk expressed as the hazard function over time will be presented graphically according to the time expressed in years and using a kernel smoothing method. A horizontal line will represent the incidence rate calculated, as number of patients with one or more events divided by the number of patients treated.

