9.5 STUDY SIZE

9.5.1 Determination of sample size

This is a descriptive study that is not testing a hypothesis and is including all patients who wish to participate. As such, a formal sample size calculation is not performed. The projected study sample size will be approximately 260 patients.

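### The horizontal 'incidence rate' line is defined as a crude proportion of patients, which conflicts with the patient-year rate in the same section and ignores unequal follow-up

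*Protocol*

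**What the plan says.** Section 9.7.1 plans two graphs for the five important identified risks. One shows cumulative risk by a life-table approach. In the other, "the instantaneous risk expressed as the hazard function over time, will be presented according to the time expressed in years". It then adds a horizontal line for the "incidence rate calculated, as number of patients with one or more events divided by the number of patients treated". The abstract repeats this under Data Analysis: "A horizontal line will represent the incidence rate calculated, as number of patients with one or more events divided by the number of patients treated". Neither place names the graph that is to carry the line.

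The next bullet of 9.7.1, limited to rare events, uses the same term in another sense: "number of patients with the event, total patients years for the event, and incidence rate per 100 patient-years with its 95% CI".

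Other parts of the protocol determine how the line would behave:
- Section 9.2.1: follow-up runs up to ten years from entry of the first patient, or to definitive removal of the pump if that comes first.
- Section 9.7.3: the cumulative cohort is analysed every year.
- Section 9.5.1: "The projected study sample size will be approximately 260 patients".
- Abstract, Study Size: "No new patient or a very limited number of newly implanted patients is expected".

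**The concern.** An incidence rate needs time at risk in its denominator, and patients with an event over patients treated has none. One section therefore gives one term two incompatible meanings, and the formula stated for the line is the one that is not a rate.

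A horizontal line beside a hazard curve is naturally read as the average hazard, so that stretches of the curve above it look like periods of raised risk. This line does not estimate the average hazard. Its height depends on how long patients happened to be followed, and follow-up is unequal here because it ends at pump removal during a phase-out. The yearly reports are timed to the periodic safety updates, so a line labelled 'incidence rate' could climb from one report to the next with no change in risk.

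**Working it through.** The protocol gives no event rate or precision figure to reproduce, so this check shows how the line behaves under stated assumptions.

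**Inputs**
- Cohort: about 260 patients with almost no new entrants (section 9.5.1 and abstract).
- Horizon: up to ten years (section 9.2.1).
- First-event hazard *h*, constant: an assumption. I use 0.03 and 0.10 per year, plus 0.05 for one comparison.
- Censoring hazard *c*, constant: an assumption. I use 0 (none) and 0.14 per year. The second is about 1/7, from the seven-year pump life given under amendment 2 in section 5. A middle value of 0.05 is used once.

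**Formulas, at time t**
- Line as defined: P(t) = h/(h+c) × [1 − exp(−(h+c)t)].
- Expected patient-years at risk per patient: Y(t) = [1 − exp(−(h+c)t)]/(h+c).
- Person-time rate: P(t)/Y(t) = h for every t and c.
- True cumulative risk, which Kaplan-Meier estimates: 1 − exp(−ht).

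**Worked cases for h = 0.03**
- c = 0, t = 5: 1 − exp(−0.15) = 13.9%; 0.139/0.03 = 4.6.
- c = 0, t = 9: 1 − exp(−0.27) = 23.7%; 0.237/0.03 = 7.9.
- c = 0.14, t = 5: (0.03/0.17) × [1 − exp(−0.85)] = 0.1765 × 0.5726 = 10.1%; 0.101/0.03 = 3.4.
- c = 0.14, t = 9: 0.1765 × [1 − exp(−1.53)] = 0.1765 × 0.7835 = 13.8%; 0.138/0.03 = 4.6.

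| h per year | Censoring per year | Line at 1 y | Line at 5 y (ratio to h) | Line at 9 y (ratio to h) |
|---|---|---|---|---|
| 0.03 | none | 3.0% | 13.9% (4.6) | 23.7% (7.9) |
| 0.03 | 0.14 | 2.8% | 10.1% (3.4) | 13.8% (4.6) |
| 0.10 | none | 9.5% | 39.3% (3.9) | 59.3% (5.9) |
| 0.10 | 0.14 | 8.9% | 29.1% (2.9) | 36.9% (3.7) |

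The line is close to the hazard only at one year. The person-time rate stays at 3 or 10 per 100 patient-years in every cell. For example, with h = 0.03, c = 0.14 and t = 9, Y = 0.7835/0.17 = 4.61 years, and 0.138/4.61 = 0.030.

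**If the line sits on the cumulative-risk graph.** The scale fits, but censored patients stay in the denominator as if fully observed. With h = 0.05, the true cumulative risk at ten years is 1 − exp(−0.5) = 39.3%. The line would be at 31.6% with c = 0.05 and at 22.4% with c = 0.14.

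**Direction over yearly reports.** With a fixed denominator the numerator can only grow, so the line cannot fall. New entrants could dilute it, but it would take very many. With h = 0.05 and 200 patients, adding 300 during year 2 (half a year's exposure each) gives [200 × (1 − exp(−0.10)) + 300 × (1 − exp(−0.025))]/500 = 5.3%, still above the 4.9% of year 1.

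**The case against.** The strongest reply is that little depends on this line. The study is descriptive with no testing, and no estimate, interval or decision rule uses it. For all five risks, section 9.7.1 gives numbers at risk, numbers of events and Kaplan-Meier probabilities with 95% confidence intervals at six months and each year. The smoothed hazard is itself per unit of time. All of this stands, and it limits the severity.

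Three stronger readings are tempting, and the protocol does not support them:
- *That the line is drawn on the hazard graph.* Neither 9.7.1 nor the abstract says so. The objection about units applies only if it is.
- *That the crude proportion is the only incidence rate planned for the common risks, such as severe hypoglycaemia.* The protocol does not define 'rare', and section 9.7 refers to an amended SAP for the full analyses. Section 9.7.2 also plans a yearly event-rate summary for selected adverse events and allows for recurrent-event methods, although neither is committed to the five identified risks.
- *That the line will overstate the rate by the full no-censoring multiples and rise every single year.* Those multiples are the upper end of the range, because follow-up stops at pump removal. The rise is an expectation, and the line stays flat in a year without new first events.

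None of this rescues the definition. On the cumulative-risk graph the line would still be mislabelled and would still fall below the Kaplan-Meier risk under censoring.

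**Conclusion.** The definition is wrong as written, in both 9.7.1 and the abstract. It is not detail left to the SAP, because the protocol states the formula. Over the assumed range of censoring, the line would stand at about 3.4 to 4.6 times a constant rate of 3 per 100 patient-years at 5 years, and 4.6 to 7.9 times at 9 years. At 10 per 100 it would read about 29-39% and 37-59%. These figures rest on constant hazards that the protocol does not supply. The direction follows from a nearly fixed denominator. A reader might infer that the primary analysis is invalid, but the Kaplan-Meier estimates do not use this line and remain sound. This is a should-fix.

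**What to change.** Change section 9.7.1 and the abstract together:
- Define the line as patients with a first event divided by total patient-years at risk up to first event or censoring.
- Express it in the unit of the hazard axis, and state that it is drawn on the hazard graph.
- Report this rate with its 95% confidence interval for all five identified risks, so that the term has one meaning throughout.
- If the crude proportion is kept, label it 'proportion of patients with at least one event' and keep it off the hazard graph.

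The cost is one sentence in two places, matching SAP text and one programming change. No new data are needed, because event and censoring dates are already required for the Kaplan-Meier analysis.
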